## **Objectives:**

- To investigate whether IICRA has the better efficacy in treating substance dependence along with comorbidities than the indoor conventional treatment for substance dependence.
- To adapt the IICRA treatment strategy grounded in Pakistani culture and religious values for the treatment of drug addicts in Pakistan.

- To determine whether IICRA treatment is more effective in treating poly drug addicts and drug addicts with or without comorbidities.
- To determine whether IICRA treatment is more effective for those addicts who were treated for one or more treatment previously as compare to those having first treatment.

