### **Research Method and Design:**

A randomized control trial was used as research method on indoor residential patients and guidelines of good clinical practices were followed (Guideline, 2001). The sample size for this clinical trial was 60 in total (30 for control group and 30 for treatment group) in order to maintain this number, the sample size was extended to 34 for each group in order to get adequate retention of the sample. The retention number of sample was 68 at the time of pre assessment and closed at 59 at the time of last follow up assessment. All participants who were admitted for treatment of SUD with or without comorbid mental disorders were recruited for research. Intervention was administered after the 21 days of detoxification. For recruitment and randomization, it was not applicable to control extraneous variables in a single facility so two sites were selected for this purpose. Selection of sites were based on minimizing extraneous variables by selecting identical residential treatment sites. One site such as Islamabad Rehab Clinic (IRC) was willing to give permission for implementation of IICRA based intervention. Hence, IRC was selected for recruiting treatment group.

Second site was considered for recruiting control group where they were giving traditional treatment in residential setting based on disease model. The site is named as Hayat Rehab Clinic (HRC). The permission for conducting research and recruiting participants were sought out from the authorities. Traditional treatment was termed as treatment as usual which includes detoxification of drugs and duration of detoxification from acute withdrawal consisted on 21 days,

During these early days focus was on adjustment to residential treatment along with hygiene and routine related compliance. Afterwards, the focus was on general counselling for drug addiction prevention, twelve steps program, habit formation based on seven habits for highly effective people and life skills training which is mainly delivered through group classes and lectures. Patients' individual sessions are also scheduled with psychologists once weekly, the focus of these individual sessions is to maximize the interaction with family through relationship building and relapse prevention skills. Duration of residential treatment is between 90-120 days.

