The treatment group received interventions based on Islamically Integrated CRA (IICRA). These sessions were divided into daily goals including counseling related to hygiene, physical activities, psychotherapy of mental disorders and drug addiction related management. After discharge from residential treatment, they were followed up for six months to check the effectiveness of IICRA in the context of relapse and recovery from SUD as well as from comorbidities. These six months follow up was consist of further three follow up sessions; first session was conducted on the discharge date from the facility, second was on fifth month and third was on sixth month following discharge.

Sample in the present study for clinical trial was based on those diagnosed individuals who were hospitalized in rehab for the treatment of SUD. Age of the sample was varying from 16 years to 60 years, where 24% individuals were from late adolescence, 39% from early adulthood and finally 37% were from middle adulthood. The chronicity of disease in the sample varies 78% of them were abusing substance between from one year to 10 years and 22% were abusing more than 10 years. Similarly, the rate of relapse or number of treatments within sample was computed as 54% individuals were hospitalized first time and 46% were hospitalized two and more than two times. Additionally, the type of substance abuse was also varying cross the

sample which included cannabis, alcohol, pills, heroin, Ice and multiple substance abuse (Alcohol, cannabis and prescribed substances) as well. The gender was mainly male in sample which was 98% and only one participant was female in the sample. Moreover, 75% individuals of the sample were diagnosed with SUDs and 25% were also having comorbid mental illness. Hence, the representativeness of the sample was limited to clinical population diagnosed with SUDs as well as comorbidities with SUDs.

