**ADAPTATION OF COMMUNITY REINFORCEMENT APPROACH FOR
THE TREATMENT OF DRUG ADDICTION**

[name]

74-FSS/PHDPSY/F-18

[name]

Associate Professor (supervisor)

Department of Psychology

Faculty of Social Sciences

International Islamic University Islamabad

July 10, 2024

Statistical Analysis Plan

The collected data for this clinical trial was analyzed using SPSS 25 version. Important statistical analysis includes independent sample t-test, paired sample t-tests and one way ANOVA was used. Following are the defining parameters.

Independent sample t-test

Independent sample t-test was used to understand the efficacy of the treatment program between control and experimental groups.

Paired sample t-test

Paired sample t-test was used to elaborate the differences between the level of assessment. In order to assess the differences on pre and post assessment of interventions based on SCL-90 (scale of comorbidity).

One way ANOVA

One way ANOVA was used to understand the differences between pre assessment, post assessment and follow up to draw conclusion about the recovery of the participants which is measured by ARQ (Addiction recovery questionnaire).

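### The SAP analyses repeated ARQ scores from the same patients with a one-way ANOVA; followed as written, the test is conservative, can miss moderate change, and does not compare the arms

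*SAP*

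**What the plan says.** Under its One way ANOVA heading the SAP states: "One way ANOVA was used to understand the differences between pre assessment, post assessment and follow up to draw conclusion about the recovery", with recovery measured by the ARQ. It mentions no repeated measures, within-subject factor, sphericity correction or mixed model. It does not say whether the arms are pooled or analysed separately.

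The SAP does distinguish independent from paired t-tests. The only outcome named under the paired test is SCL-90. The between-arm test reads "Independent sample t-test was used to understand the efficacy of the treatment program between control and experimental groups" and names neither outcome nor time point.

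The Protocol (Research Method and Design) describes one cohort followed over time. The sample was "68 at the time of pre assessment and closed at 59 at the time of last follow up assessment", and "These six months follow up was consist of further three follow up sessions; first session was conducted on the discharge date from the facility", with the others at months five and six. The first objective is comparative: "To investigate whether IICRA has the better efficacy in treating substance dependence along with comorbidities than the indoor conventional treatment for substance dependence".

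**The concern.** A one-way ANOVA without a within-subject factor treats the occasions as separate groups of people. Here they are the same people, so stable differences between patients inflate the error term although they play no part in the change over time. With positive correlation between a patient's scores, this does not create false claims of change. It costs power, and a null result could be read as no recovery. The SAP draws its recovery conclusion from this test.

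A second point has nothing to do with power. The ANOVA as described contains no arm term, so a significant result says that scores changed over time. It would be significant if both arms improved equally, and so cannot by itself serve the first objective.

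**Working it through.** **Inputs from the documents.** There are three occasions (k = 3; SAP). The Protocol gives 68 patients at pre assessment and 59 at last follow-up. The arm counts agree: control 34 − 3 − 1 − 2 = 28, experimental 34 − 2 − 1 = 31, and 28 + 31 = 59.

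**Assumed, because not given.** Alpha 5%; within-patient correlation ρ = 0.3, 0.5, 0.7; compound symmetry (CS) or AR(1); means (0, d, d) in SD units, that is, a gain by post assessment that is sustained.

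There is no plan figure to reproduce. The sample size of 60 comes without alpha, power, effect or SD.

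**The two tests.**
- One-way: F = [SS_time/(k−1)] / [SS_within/(k(n−1))]
- Repeated-measures: F = [SS_time/(k−1)] / [SS_residual/((k−1)(n−1))]

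Under CS with no true change, the numerator has expectation σ²(1−ρ). The repeated-measures denominator has the same expectation; the one-way denominator has σ². The one-way ratio therefore centres on about 0.7, 0.5 or 0.3 instead of 1.

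**True error rate.** For n = 59 the one-way critical value (2 and 174 df) is 3.05. Holding the denominator at σ², the rejection rate is about exp(−3.05/(1−ρ)):
- ρ = 0.3: exp(−4.36) = 1.3%
- ρ = 0.5: exp(−6.10) = 0.2%
- ρ = 0.7: exp(−10.17) = 0.004%

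Simulation (20,000 trials per setting) gives 1.5%, 0.3% and 0.01%. Under AR(1) it gives about 2.3%, 0.8% and 0.1%. Repeated-measures with Greenhouse-Geisser correction stays at 4.2 to 5.0%.

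**Power for a sustained 0.4 SD gain.** For repeated measures under CS, the noncentrality is λ = n(2/3)d²/(1−ρ). With n = 59, 59 × 0.1067 = 6.29, so λ = 8.99, 12.59 and 20.98. The noncentral F with 2 and 116 df gives 76%, 89% and 99%, in line with the simulated values below. Each cell shows one-way v the correct analysis.

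| Setting | ρ = 0.3 | ρ = 0.5 | ρ = 0.7 |
|---|---|---|---|
| Pooled completers, n = 59, CS | 59 v 75% | 58 v 89% | 57 v 99% |
| Pooled completers, n = 59, AR(1) | 58 v 69% | 57 v 80% | 56 v 94% |
| All scores 68/63/59, CS | 65 v 80% | 65 v 91% | 66 v 99% |
| All scores 68/63/59, AR(1) | 64 v 73% | 63 v 84% | 63 v 97% |
| Experimental arm only, n = 31, CS | 28 v 44% | 24 v 59% | 17 v 82% |
| Control arm only, n = 28, CS | 25 v 40% | 19 v 54% | 13 v 78% |

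In the all-scores rows the comparator is a mixed model with known covariance and random dropout, which is slightly optimistic. The 63 at post is assumed: 68 less the five treatment withdrawals. In the other rows the comparator is repeated-measures with Greenhouse-Geisser. The per-arm rows are a reading the SAP does not state.

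**Other gains.** On pooled completers the one-way test has about 80 to 90% power at 0.5 SD, 94 to 99% at 0.6 SD and about 100% at 0.8 SD. Per arm at 0.8 SD it has 88 to 98%. Smaller or gradual gains fare worse: pooled, CS, ρ = 0.5, a sustained 0.3 SD gain gives 26 v 65%, and a linear 0.5 SD gain 69 v 94%.

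**Attribution.** If both arms gained the same 0.6 SD, so that IICRA had no advantage, the pooled one-way ANOVA would still be significant 94 to 99% of the time.

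**Power of arm x time at 31 v 28 (CS).** λ = (31 × 28/59)(2/3)d²/(1−ρ). For d = 0.4, 14.71 × 0.1067 = 1.57, so λ = 2.24, 3.14 and 5.23. With 2 and 114 df, power is 24%, 33% and 51%. For d = 0.8, λ = 8.97, 12.55 and 20.92, and power is 76%, 89% and 99%.

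**The case against.** The strongest reply is that the term counts factors: a one-factor repeated-measures ANOVA is also one-way. The SAP is a short past-tense summary, it never says the occasions were treated as independent, and its paired t-test opens with a general reference to assessment levels before naming SCL-90. Its authors evidently knew about pairing. This stands as a limit: the wording is wrong or incomplete, but it does not prove which SPSS procedure was run. It does not clear the text, because a reader who follows the SAP would run the independent-groups test.

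Second, the error is in the safe direction. If the ANOVA was significant, the conclusion of change over time stands. Harm requires that the independent procedure was run, gave a null result, and was read as no recovery. That also stands, with the proviso that it depends on positive correlation. At ρ = 0 the two tests agree; at ρ = −0.2 the one-way test is liberal (8.0% at n = 28).

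Third, the SAP assigns efficacy between arms to the t-test, not to the ANOVA, so the missing arm term is a separate matter. That is fair as far as it goes. But the t-test names no outcome or time point, so no analysis in the SAP is specified for comparing ARQ change between arms. This gap remains even if repeated measures was meant.

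**Conclusion.** The concern holds and should be fixed. As written, the SAP names a test with the wrong error term for the ARQ. Confidence is high that the text names the wrong test, and moderate that the wrong procedure was run.

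On the plainest reading (arms pooled), the cost is confined to moderate, small or gradual gains: at a sustained 0.4 SD, 56 to 59% power against 69 to 99%. Sustained gains of 0.6 SD or more are found either way. The larger per-arm losses apply only if the arms were analysed separately. All sizes rest on the assumed alpha, correlations and effects. Whichever procedure was run, a test of time alone does not answer the comparative objective.

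**What to change.** Replace the one-way ANOVA with a linear mixed model for ARQ: patient as the repeated unit, fixed effects for arm, time and arm x time, and all available scores. This keeps the earlier scores of the nine patients lost by last follow-up (68 − 59). State its missing-data assumption, since the losses include withdrawals and a death. A repeated-measures ANOVA with arm as between-subject factor and Greenhouse-Geisser correction is an acceptable alternative.

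Report arm x time with its confidence interval. At 31 v 28 a non-significant result is weak evidence of no difference, as the power figures above show.

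The text should also:
- state which ARQ occasions are used, since the SAP lists three levels and the Protocol lists three follow-up sessions without saying whether ARQ was given at each;
- state whether any per-arm analysis was done;
- name the outcome and time point of the between-arm t-test;
- say that arm x time does not remove the confounding of arm with site: "IRC was selected for recruiting treatment group", while "Second site was considered for recruiting control group".

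Because the SAP is in the past tense, label the result a corrected analysis.

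Cost: one paragraph of SAP text and a rerun in the same package on the same data. If a repeated-measures ANOVA was already run, only the wording changes and the arm x time test is added.

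### The ANOVA from which the SAP concludes recovery cannot tell a sustained gain from improvement followed by full relapse, and the SAP names no follow-up contrast that could

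*SAP*

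**What the plan says.** Under its One way ANOVA heading the SAP says that the test was used to examine "differences between pre assessment, post assessment and follow up to draw conclusion about the recovery of the participants". The outcome is the ARQ. No pairwise comparison, contrast, direction of scoring or definition of recovery follows.

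The other two tests in the SAP do not fill the gap:

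- The paired t-test is described for "differences on pre and post assessment of interventions based on SCL-90 (scale of comorbidity"), so it is tied to another scale and stops at the post assessment.
- For the between-arm test the SAP says only: "Independent sample t-test was used to understand the efficacy of the treatment program between control and experimental groups". It gives no outcome and no time point.

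The protocol (Research Method and Design) explains why patients were followed after discharge: "they were followed up for six months to check the effectiveness of IICRA in the context of relapse and recovery from SUD". The visits are set out as "first session was conducted on the discharge date from the facility, second was on fifth month and third was on sixth month following discharge". The SAP does not say which of these is its follow-up level, or whether its post level is the discharge visit.

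**The concern.** An overall F-test over three assessments asks whether the three means are all equal. It has no sign and does not say which assessment differs. ARQ scores that rise during residence and then fall back to the admission level violate equality just as much as scores that rise and stay up.

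The follow-up period exists to separate those two courses. If a significant F is taken as evidence of recovery, a group that relapsed completely can be reported as recovered. Treating the data correctly as repeated measures does not remove the problem. It makes the test more sensitive to either pattern and still does not distinguish them.

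**Working it through.** The plan has no figure of its own to reproduce here: it states no alpha, effect size, ARQ standard deviation or power.

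**Inputs from the documents.** Three assessment levels (SAP). Completers: 31 of 34 in the treatment group and 28 of 34 in the control group, 59 in all (Protocol, Research Method and Design).

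**Assumptions.** Two-sided alpha 0.05; d = 0.3, 0.5 or 0.8 SD; within-patient correlation ρ = 0.5, varied from 0.3 to 0.7; equal n at each assessment.

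**Step 1: the two profiles look alike to F.** The noncentrality depends on the sum of squared deviations of the means from their average.

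- Full relapse (0, d, 0): average d/3, so d²/9 + 4d²/9 + d²/9 = (2/3)d².
- Sustained gain (0, d, d): average 2d/3, so 4d²/9 + d²/9 + d²/9 = (2/3)d².
- Lasting deterioration (0, −d, −d): also (2/3)d².

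The sums are identical, so the power is identical whatever d is. This step needs no assumed effect size.

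**Step 2: how often F is significant under full relapse, n = 31.**

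- Independent levels: λ = n(2/3)d², df 2 and 3(n − 1) = 90. λ = 1.86, 5.17 and 13.23 for the three values of d.
- Repeated measures: λ = n(2/3)d²/(1 − ρ), df 2 and 2(n − 1) = 60. With ρ = 0.5, λ = 3.72, 10.33 and 26.45.
- Ordinary one-way ANOVA applied to the same 31 patients' correlated scores: by simulation with ρ = 0.5, because the F distribution no longer applies.

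| d (SD) | Repeated measures, ρ = 0.5 | Ordinary ANOVA, correlated scores, ρ = 0.5 | Ordinary ANOVA, independent levels |
|---|---|---|---|
| 0.3 | 37% | about 9% | 21% |
| 0.5 | 81% | about 45% | 50% |
| 0.8 | 99.7% | about 95% | 90% |

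The last column would need a separate group of 31 at each assessment. It is a reference only, since here the same patients are measured repeatedly.

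**Step 3: sensitivity.**

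- Repeated measures, n = 31, ρ from 0.3 to 0.7: 28% to 58% at d = 0.3, and 66% to 96% at d = 0.5.
- n = 28, d = 0.8: 99% for repeated measures (ρ = 0.5), 87% for independent levels.
- All 59 pooled, d = 0.5: 98% and 80% respectively.

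**Step 4: a direct contrast.** Under (0, d, 0) the true follow-up minus pre difference is 0, so a two-sided 5% paired test is significant in the favourable direction in about 2.5% of trials, whatever d is. Simulation with n = 31 and ρ = 0.5 gives 2.3% to 2.6% for d from 0.5 to 1.0. Under sustained recovery (0, 0.8, 0.8) the same contrast is significant in 99%.

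**The case against.** The strongest reply is that reliance on F alone is inferred from silence. The SAP introduces its list as the important analyses, so the list need not be complete. An analyst would normally look at the means or run pairwise comparisons, and a relapse would then be visible. The paired t-test is also introduced in general terms, as a way to examine differences between assessment levels. This stands in part. The documents do not show that anyone will conclude recovery from a p-value alone. They show only that nothing else is specified for the ARQ. The general phrase about paired tests is followed at once by SCL-90 pre and post, and that is its natural scope.

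A second reply is that the size of the problem is unknown. That also stands. A reader might infer that the test will be significant whenever patients relapse. The documents do not support this: it can be, with a probability that depends on quantities they do not give, and at d = 0.3 that probability is modest.

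A third reply is that the first objective is IICRA against conventional treatment, which the SAP assigns to the between-arm t-test. That is correct, and this point does not show that the efficacy comparison fails. But that test has no stated outcome or time point. Even if applied to the ARQ at follow-up, it would compare arms and would not show that gains over admission had lasted.

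Finally, it is tempting to equate the SAP's post assessment with discharge. The protocol counts discharge as the first follow-up session, and the SAP lists post and follow-up separately, so the mapping has to be stated by the sponsor.

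**Conclusion.** The concern holds in this form: the one stated ARQ analysis responds equally to full relapse and to sustained gain, so its significance does not by itself license the recovery conclusion the SAP attaches to it. The equality is exact for equal n per assessment. It would be only approximate for an ordinary ANOVA that used unequal numbers, such as 68 at pre and 59 at the end.

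The probabilities are illustrations under assumed d and correlation, not estimates for this trial. The defect is present whether the ANOVA is run by arm or pooled, and as ordinary or repeated measures. It should be corrected before any statement about recovery is made from the ARQ.

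**What to change.** Replace the F-test as the basis for the recovery conclusion with two within-patient ARQ contrasts, each with a 95% confidence interval, reported by arm and compared between arms:

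1. **Recovery: month 6 minus pre.** Conclude recovery only if the interval excludes zero in the direction the ARQ scores as improvement. State that direction.
2. **Maintenance: month 6 minus post.** First state whether post is the discharge visit. Report the estimate and interval beside contrast 1. An interval that includes zero does not prove that gains were kept.

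Report month 5 alongside, keep the F-test as descriptive, and say which patients enter each contrast.

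Both documents are written in the past tense and follow-up has closed, so the contrasts must be labelled as added after data collection and not presented as prespecified. That post hoc status is the main drawback. Otherwise the cost is one SAP paragraph and a rerun on data already held.
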